### **2.2 Secondary Objectives**

1. To determine the proportion of prolonged ileus (> 7 days) in each group
2. To determine the time to return of bowel function components in each group: time to first flatus, time to first bowel movement, time to tolerance of solid food
3. To determine the time to hospital discharge order written in each group
4. To measure the adverse event rate in each group
5. To perform subgroup analyses on each group: 0 vs. 1 or greater anastomoses, 0 vs. 1 or greater visceral resection, high vs. low amount of postoperative narcotic use (above or below the median total postoperative morphine equivalent dose of narcotics), epidural vs. no epidural

## 2.3 Endpoints

### Primary Endpoint:

The time to return of upper and lower GI function (GI-2) will be measured as follows:

- Time measured in hours from the time leaving the operating room to the later of the following two events:
  - i. Time that the patient first tolerates solid food
  - ii. Time that the patient first passes a bowel movement
- If upper and lower GI function have not occurred by the time of discharge, the patient will be censored.

### Secondary Endpoints:

1. Prolonged ileus will be measured by the proportion of patients who do not pass flatus or bowel movement greater than 7 days from the time of surgery
2. The time to return of bowel function components will be measured in hours from the time leaving the operating room until:
  - The time to first flatus
  - The time to first bowel movement
  - The time to tolerance of solid food
3. The time to hospital discharge order written will be measured in hours from the time leaving the operating room
4. Adverse events will be measured using CTCAEv3 criteria.
5. Primary and secondary endpoints will be measured in each subgroup

## 3.0 PATIENT ELIGIBILITY

---

### 3.1 Inclusion Criteria

Subjects must meet all of the inclusion criteria to participate in this study.

1. Ability to understand and the willingness to sign a written informed consent.
2. Scheduled to undergo open (non-minimally invasive) CRS/HIPEC.
3. Scheduled to receive postoperative pain management with intravenous opioids.
4. Age  $\geq$  18 years.
5. Eastern Cooperative Oncology Group (ECOG) Performance Status  $\leq$  2.
6. Women of child-bearing potential with negative pregnancy test prior to initiating study drug dosing.

### 3.2 Exclusion Criteria

Subjects meeting any of the exclusion criteria at baseline will be excluded from study participation.

1. Greater than 7 days of consecutive opioid use immediately prior to scheduled surgery.
2. Child-Pugh Class C hepatic impairment.
3. End-stage renal disease (GFR < 15 mL/min/1.73 m^2 and/or on peritoneal dialysis or hemodialysis).
4. Complete mechanical bowel obstruction.
5. Contraindication or inability to tolerate oral medication postoperatively.
6. Presence of gastrointestinal ostomy after CRS/HIPEC.
7. Pancreatic or gastric anastomosis performed during CRS/HIPEC.
8. History of allergic reactions or hypersensitivity attributed to compounds of similar chemical or biologic composition as alvimopan at the treating investigators discretion.
9. Severe or uncontrolled medical disorder that would, in the investigator's opinion, impair ability to receive study treatment (i.e. uncontrolled diabetes, chronic renal disease, chronic pulmonary disease or active, uncontrolled infection, psychiatric illness/social situations that would limit compliance with study requirements).
10. History of myocardial infarction in the 12 months prior to scheduled surgery.
11. Pregnant or nursing.

#### **4.0 TREATMENT PLAN**

---

##### **4.1 Treatment Dosage and Administration**

Participants will receive alvimopan (or placebo) preoperatively, then every day after surgery until hospital discharge or for a maximum of 7 days.

Twelve (12) mg of alvimopan (or placebo) will be given by mouth in the preoperative holding area 30 minutes to 5 hours prior to surgery. The treatment will continue at a dose of 12 mg BID by mouth starting on postoperative day (POD) 1 for the earlier of seven days or hospital discharge, as defined by GI-2 (later of time of tolerance of solid diet or bowel movement), for a maximum of 15 total doses. In patients with a gastrostomy tube in place, this will be clamped for 1 hour after administration of the study drug per standard of care for oral medication administration in a patient with a gastrostomy tube. Documentation of gastrostomy tube clamping after study drug administration will be made in the medical record by nurses according to the standard of care nursing policies and usual practices of each nursing unit. The study drug (alvimopan or placebo) will be administered in the hospital by the patient's nurse.

Agent	Dose	Route	Schedule
Alvimopan	12 mg	PO	30 minutes – 5 hours prior to surgery, then twice daily (BID) starting POD 1 for a maximum of 7 days or until hospital discharge
Placebo	NA	PO	30 minutes – 5 hours prior to surgery, then twice daily (BID) starting POD 1 for a maximum of 7 days or until hospital discharge

#### **4.2 Permitted concomitant therapy**

Medications used to treat typical postoperative symptoms are permitted, as clinically indicated. This includes, but is not limited to, analgesics (local, regional and systemic; narcotics, non-steroidals, and local anesthetics), antiemetics, and anti-pruritics. These are all given per standard of care, and at the discretion of the treating clinicians.

#### **4.3 Prohibited concomitant therapy**

Participants with greater than seven days of consecutive opioid use immediately prior to the date of surgery (CRS/HIPEC) are ineligible for the study. Any other use of preoperative opioids may be used with caution, at the investigator's discretion.

#### **4.4 Other Modalities or Procedures**

After CRS/HIPEC, participants will undergo a standardized postoperative care pathway, which is the standard of care at our institution. This includes use of epidural analgesia, early mobilization and ambulation on POD 1-2, liquid diet on POD 1-3, early removal of the foley catheter, and clamping trials of the gastric tube (if present) once bowel function returns.

#### **4.5 Toxicities and Dosing Delays/Dose Modifications**

Any patient who receives treatment on this protocol will be evaluable for toxicity. Each patient will be assessed for the development of toxicity according to the NCI Common Toxicity Criteria for Adverse Events (CTCAE), version 4.03. Dose adjustments are not applicable in this study and will not be made. Participants who have emesis within one hour after taking the study medication or have visible study medication within the gastric tube effluent or who otherwise miss a dose for any other reason, will not be re-dosed, and they will resume standard dosing at the next scheduled dose. Participants or providers may decide to cease the study medication before all doses have been administered per the criteria listed in Section 4.6.

#### **4.6 Duration of Therapy**

In the absence of treatment delays due to adverse events, treatment may continue for a maximum of **seven days** or less if one of the following occurs:

- Participant is discharged home prior to seven days after surgery

- Inter-current illness that prevents further administration of treatment (i.e. participant is unable to tolerate oral medication with gastric tube clamped or the participant is intubated and cannot take oral medication). Participants may resume study drug administration once it can be tolerated without “make-up” doses given (i.e. no study drug will be given beyond postoperative day seven). If more than 50% of the doses are missed, then the participant will be withdrawn from the study (see Section 5.5).
- Unacceptable adverse event(s)
- Participant decides to withdraw from the study, **OR**
- General or specific changes in the patient’s condition render the patient unacceptable for further treatment in the judgment of the investigator.

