### **5.5 Removal of Subjects from Study Treatment and Study**

Patients can be taken off the study treatment and/or study at any time at their own request, or they may be withdrawn at the discretion of the investigator for safety, behavioral or administrative reasons. The reason(s) for discontinuation will be documented and may include:

**5.5.1** Patient completed study treatment;

**5.5.2** Patient voluntarily withdraws from treatment (follow-up permitted);

**5.5.3** Patient withdraws consent (termination of treatment and follow-up);

**5.5.4** Patient is unable to comply with protocol requirements (i.e. the patient is unable to tolerate or misses more than 50% of the study drug doses);

**5.5.5** Patient experiences toxicity that makes continuation in the protocol unsafe;

**5.5.6** Treating physician judges continuation on the study would not be in the patient's best interest;

**5.5.7** Patient becomes pregnant (pregnancy to be reported along same timelines as a

serious adverse event);

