### **9.8 Interim analysis**

When the 64th subject has reached the primary endpoint (or been censored because of loss to follow-up), a futility analysis will be performed.

The futility analysis will use a stochastic curtailment approach (Crowley and Anhkerst, Clinical Trials in Oncology, 2nd ed p 233), as computed in PASS 14.0.6. If at the interim analysis, the conditional power (i.e. the probability that the study will go on to reject the null hypothesis, given the observed data at the interim analysis) is below 20%, the study will stop. This futility analysis will be carried out by the statisticians at the MCC Biostatistics Shared Resource, using a one-sided logrank test at the 5% significance level.

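### Section 4.6 withdraws participants from the study for missed doses, and the plan does not say whether GI-2 is still collected or how it is then analysed

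*Combined protocol and SAP*

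**What the plan says.** - **Section 4.6, Duration of Therapy.** The bullet on inter-current illness gives as its examples: "participant is unable to tolerate oral medication with gastric tube clamped or the participant is intubated and cannot take oral medication". Dosing may resume without make-up doses. The bullet then states: "If more than 50% of the doses are missed, then the participant will be withdrawn from the study (see Section 5.5".
- **Section 5.5, Removal of Subjects.** "Patients can be taken off the study treatment and/or study at any time at their own request", and otherwise "they may be withdrawn at the discretion of the investigator for safety, behavioral or administrative reasons". Item 5.5.4 repeats the threshold ("the patient is unable to tolerate or misses more than 50% of the study drug doses") with no word on follow-up. Item 5.5.2 does address it ("Patient voluntarily withdraws from treatment (follow-up permitted"). Item 5.5.3, withdrawal of consent, is the only listed reason said to end both treatment and follow-up.
- **Section 2.3, primary endpoint.** "If upper and lower GI function have not occurred by the time of discharge, the patient will be censored". This is the only censoring rule in the endpoint definition.
- **Section 9.8.** Another reason for censoring appears only in the interim trigger, when the 64th subject "has reached the primary endpoint (or been censored because of loss to follow-up), a futility analysis will be performed".
- **Section 9.4.** mITT requires one dose and one efficacy evaluation after baseline. The 50% dose threshold enters only the per-protocol definition. Withdrawn subjects are named only under the safety population. The primary analysis uses mITT without imputation; multiple imputation is a sensitivity analysis, with no model given.
- **Section 4.4.** Clamping trials of a gastric tube begin when bowel function returns.

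**The concern.** Leaving study drug and leaving the study have different consequences for a time-to-event endpoint. A patient who stops study drug but stays under observation still supplies a GI-2 time. A patient withdrawn from the study may not, and 4.6 uses the second wording.

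The circumstances that cause the missed doses are not obviously independent of the outcome. A patient who cannot tolerate a clamped tube is plausibly one whose bowel has not recovered, and 4.4 itself ties clamping to recovery. If GI-2 observation stops there, slow recoverers are removed from the risk set early. The log-rank test assumes that censored patients have the same prospects as those still at risk; here they would have worse ones. Times to recovery would then look too short and power would fall. If the loss differed between arms, the comparison itself would be biased.

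**Working it through.** **1. The plan's own figures.** Inputs from Section 9.2: hazard ratio 1.59, one-sided 5%, 80% power, n = 122, 5% drop-out, 128 enrolled, medians 9 and 5.7 days.
- Freedman: (1.645 + 0.842)² × (2.59/0.59)² ≈ 119, or 120 in even numbers, against 122 stated. This is close.
- Drop-out: 122/0.95 = 128.4, against 128 stated.
- Alvimopan median: 9/1.59 = 5.66 days, against 5.7 stated.

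**2. When the threshold can be crossed.** Section 4.6 gives no denominator. Assume the 15-dose maximum of Section 4.1; more than half is then 8 doses.
- Preoperative dose taken and every later dose missed: 2 × 4 = 8, so the end of POD 4.
- First postoperative dose also taken: 1 (POD 1) + 6 (POD 2–4) + 1 (POD 5) = 8, so POD 5.
- Latest: POD 7.

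**3. Does this come before GI-2?** With exponential times, the share not yet recovered at day t is 0.5^(t/median).

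| Day | Control (median 9) | Alvimopan (median 5.66) |
|---|---|---|
| 4 | 73% | 61% |
| 5 | 68% | 54% |
| 7 | 58% | 42% |

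Withdrawal can therefore precede the endpoint.

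**4. Size, by simulation.** The documents give no missed-dose rate, so the loss rates are assumptions. Settings:
- one-sided 5% log-rank test, 61 per arm, 20,000 trials per setting, Monte Carlo error about 0.3 points;
- exponential times (medians 9 and 5.66 days) and Weibull shape 2 (medians 9 and 9/√1.59 = 7.1 days), both with hazard ratio 1.59;
- a given share of patients whose GI-2 would exceed 10 days (the typical stay in Section 4.7) is censored at day 4, 5 or 7.

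Beyond 10 days lie 43–46% of control and 26–29% of alvimopan patients. Losing 10% of them means 4–5% of control and about 3% of alvimopan patients.

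| Share of slow recoverers lost, same in both arms | Control lost | Alvimopan lost | Power |
|---|---|---|---|
| none | 0 | 0 | 81% |
| 10% | 4–5% | 3% | 78–80% |
| 25% | 11–12% | 6–7% | 74–77% |
| 50% | 21–23% | 13–15% | 64–72% |

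Type I error, using the control distribution in both arms, stays near 5% in every row.

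Unequal loss:
- 25% of slow placebo and 10% of slow alvimopan patients lost: type I error 2.7–4.2%, power 66–75%.
- The reverse: type I error 6.6–9.5%, power 81–85%.

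**5. How to read these numbers.** Loss is selected directly on the outcome, which is near a worst case. The 61 per arm already sets aside the drop-out allowance; if nothing else uses it (64 per arm), 10% loss leaves power at about 80–81%, the design target. The 50% row loses over four times the planned 5% among controls and is shown only as a bound.

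**The case against.** **Section 5.5 can be read as keeping these patients in follow-up.** Only consent withdrawal (5.5.3) is said to end follow-up, and 4.6 refers to 5.5, so a natural joint reading is that missed doses do not stop data collection. That stands as one reading. But 5.5.4 is silent, and 4.6 is mandatory and refers to the study, so the text does not settle it.

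**Section 9.4 already keeps them.** With no dose minimum in mITT, patients below 50% are in the primary population if they have one efficacy evaluation. A reader might infer that 4.6 contradicts 9.4. It does not: a withdrawn patient can remain in mITT with the data collected so far. The tension is one of intent, and naming withdrawn subjects only under safety does not exclude them from mITT.

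**The group is narrow.** Exclusion 5 and the POD 1 eligibility recheck should remove patients who cannot take oral drug from the start. A reader might also take 4.6 to apply to anyone who misses half the doses, but its sentence sits in the inter-current-illness bullet. The general threshold is in 5.5.4, where withdrawal is discretionary.

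**The link to slow recovery is only partly documented.** Section 4.4 supports it for tube clamping. A tube alone does not cause missed doses, since it is clamped for an hour after each one, and nothing ties intubation to GI-2. The link is plausible, not shown.

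**Records and safeguards exist.** Patients are seen daily (4.7), the inpatient record is used to audit the diary (6.1), and exclusions are decided blinded (9.3). These limit the practical risk. They do not say that GI-2 is recorded after withdrawal, and the 9.3 decisions are case by case.

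**Conclusion.** The concern holds as a gap in the wording that should be fixed. Section 4.6, taken literally, can end GI-2 observation for reasons plausibly tied to slow recovery. Section 5.5 does not resolve this, and no passage says how GI-2 is handled after study withdrawal before discharge. Within the planned 5% drop-out the cost is small: about 1 to 3 points of power with 61 per arm. It reaches about 4 to 7 points if a quarter of slow recoverers are lost. These figures rest on assumed loss rates, a 15-dose denominator and selection on GI-2 beyond 10 days.

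Three stronger readings are not supported:
- **That the plan has no censoring rule.** Section 2.3 censors at discharge; what is missing is a rule for study withdrawal before discharge.
- **That the rule favours alvimopan.** Type I error rises only if more slow recoverers are lost on alvimopan. Section 1.2 reports less nausea and vomiting on alvimopan in earlier trials, which would point the other way, but it does not measure missed doses here. The direction is unknown.
- **That power would fall to about 60%.** That needs half of slow recoverers lost and also omitted from the analysis altogether, which takes more than 4.6 itself: no efficacy evaluation, or an exclusion under 9.3.

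**What to change.** - **4.6 and 5.5.4:** reconcile the two, and state in both that, whatever is decided about study drug, GI-2, its components, time to discharge order and adverse events continue to be collected from the existing diary and inpatient record unless consent is withdrawn.
- **9.4:** confirm that these participants are analysed in mITT with their observed GI-2 times, censored at discharge under 2.3 if GI-2 is not reached, and that the 50% threshold defines only the per-protocol population.
- **2.3:** add that GI-2 is censored at the time consent is withdrawn, if not yet reached.

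Whether study drug stops at this threshold is for the sponsor to reconcile between 4.6 and 5.5; no rule is proposed here.

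The cost is wording in four sections and continued use of records already kept. There is no new visit or procedure and no change in sample size.

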#### 4.7 Duration of Follow Up

Participants will be monitored daily during their postoperative stay by nurses and physicians, per standard of care after CRS/HIPEC. Typical length of stay after this procedure is 10 days. After discharge, participants will be followed (by postoperative visit or telephone call) for 30 days from the date of surgery for adverse events.

### 5.0 STUDY PROCEDURES

---

#### 5.1 Schedule of Events

	Screening (POD -30 to -1)	Preoperative Day (POD -3 to -1)	Postoperative Admission (POD 1 – Date of Discharge)	Postoperative Clinic Visit ± 5 days	Follow-up visit (POD ≥ 30) 
Assessment					
Informed consent	X				
Medical history	X				
Physical exam, including vitals 	X				
Demographic	X				
Eligibility Criteria	X				
ECOG	X				
Adverse events 			X	X	X
Concomitant medications 	X	X			
Confirmation that CRS/HIPEC performed and eligibility criteria still met 			X		
Assessment of return of bowel function 			X		
Alvimopan administration 		X	X		
Urine Pregnancy Test 	X				

By standard of care clinic visit, or telephone call if no clinic visit at this time (≥ 30 days)

after surgery)

Physical exam and vital signs: consist of temperature, heart rate, respiration and blood pressure.

Adverse events: to be collected once patient signs consent form. See Section 7 for more information.

Concomitant medications: to be collected for any subject being followed for a Serious Adverse Event (SAE) occurring up to 30 days after last dose of study drug until resolution of the SAE. (see Section 7).

Confirmed on POD 1, prior to administration of first postoperative dose of study medication.

Includes recording the date and hour of the time of first flatus, bowel movement, and tolerance of solid food (per participant diary); as well as the date/hour of leaving the operating room

Alvimopan administration: see section 8.1 for instructions on administration.

Pregnancy test: A serum or urine pregnancy test is required for all females of childbearing potential.

## **5.2 Screening/Baseline Procedures**

Assessments performed exclusively to determine eligibility for this study will be done only after obtaining informed consent. Assessments performed for clinical indications (not exclusively to determine study eligibility) may be used for baseline values even if the studies were done before informed consent was obtained.

The screening procedures include:

### **5.2.1 Informed Consent**

### **5.2.2 Medical history**

Complete medical, surgical and oncology history as well as history of infections will be obtained at screening. Any changes from Screening (e.g. worsening severity or abnormal findings) are considered to be adverse events (AEs).

### **5.2.3 Demographics**

Demographic information to be collected at screening will include date of birth, gender, race, and ethnicity.

### **5.2.4 Review subject eligibility criteria**

Review of eligibility criteria as described in Section 3 to ensure subject qualification for study entry.

### **5.2.5 Review previous and concomitant medications**

All prior medication taken by the subject within 4 weeks before starting the study is to be recorded. Concomitant medications taken by the subject during the study are to be recorded up until 30-days after last study dose. If a reportable adverse event (see Section 7) occurs within 30-days after last study dose, recording of concomitant medications should continue until resolution of the adverse event.

### **5.2.6 Physical exam including vital signs, height and weight**

Physical exam will include collection of vital signs (temperature, pulse, respirations, blood pressure), height, weight.

### **5.2.7 ECOG performance status**

ECOG performance status will be evaluated prior to study entry.

#### **5.2.8 Adverse event assessment**

Baseline assessment of subject status for determining adverse events. See Section 7 for Adverse Event monitoring and reporting.

#### **5.2.9 Pregnancy test (for females of child bearing potential)**

See section 3.1 for definition.

### **5.3 Procedures During Treatment**

Treatment will be administered in the hospital in the postoperative recovery period. There are no additional procedures or visits performed during the treatment period. However, there are some additional data collected during this period, as follows:

#### **5.3.1 Date and Time of Completion of Operation**

- To be determined from the electronic medical record (Time is the “Out of Room” time recorded in the chart).

#### **5.3.2 Total Opioid Consumption**

- To be measured in morphine equivalents, calculated after discharge.

#### **5.3.3 Assessment of Bowel Function**

- To be recorded in patient postoperative bowel function diary (Appendix B)
- An audit of at least 10% of all diaries will be undertaken to compare the patient recorded date of first recorded bowel movement with that from the electronic medical record.

